5. SAMPLE SIZE DETERMINATION

This study will be conducted in male and female subjects with a confirmed diagnosis of WAIHA. Subjects will be enrolled only once in the study and will not be included in subsequent dosing cohorts. Subjects who withdraw for any reason other than an AE may be replaced.

Formal sample size calculations were not performed. The number of subjects was chosen based on feasibility and was considered sufficient to meet the study objectives.

6. PROGRAMMING SPECIFICATIONS

The programming specifications, including the mock-up analysis tables, figures, and data listings, as well as the derived database specifications, will be prepared in stand-alone documents. The programming specification documents will be finalized prior to database lock. Footnotes in listings will reference datasets used in the listing. Footnotes in tables and figures will reference the appurtenant listings.

7. INTERIM ANALYSIS

No interim analysis is planned. Safety results will be examined for making dose-escalation decisions; no statistical analyses are planned for aiding these dose-escalation decisions.

8. APPENDICES

Appendix A: Study Assessment

Table 2. Study Assessments for Cohort 1

Visit Number	Screening	Treatment Period										Follow-Up						
	1	2	3	4	5	6	7	8	9	10	11	12	13	14	15	16	17	18 (or ET)
Time Point (Study Day)	-14 to -1	0	1 (±1 h)	2 (±2 h)	5 ^a (±4 h)	7 (±6 h)	12 ^a (±6 h)	14 (±6 h)	19 ^a (±6 h)	21 (±6 h)	28 (±6 h)	29 (±1 h)	30 (±2 h)	33 (±4 h)	42 (±3 d)	56 (±5 d)	84 (±5 d)	112 (±5 d)
Informed consent	X																	
Demographics/medical history	X																	
Inclusion/exclusion	X																	
Physical examination ^b	X	X				X		X		X	X				X	X	X	X
Vital signs ^c	X	X	X	X	X	X	X	X	X	X	X	X	X	X	X	X	X	X
Karnofsky Performance Scale	X																	
Pulse oximetry ^d		X				X		X		X	X							
Clinical safety labs ^e	X	X				X		X		X	X			X	X	X	X	X
Pregnancy test ^f	X	X														X		X
Hepatitis and HIV antibody screen	X																	
12-lead ECG ^g	X	X					X				X					X		
Tetanus and VZV antibodies ^h		X														X	X	X
Cold agglutinins (titer and thermal amplitude)		X												X		X	X	X
PK sampling ⁱ		X	X	X	X						X	X	X	X				
Immunogenicity ^j		X						X			X					X	X	X
Study drug administration ^k		X				X		X		X	X							
Immunoglobulins ^l	X	X	X	X	X	X	X	X	X	X	X	X	X	X	X	X	X ^m	X ^m
CIC		X			X	X	X	X	X	X	X			X	X	X	X	X
Haptoglobin	X	X				X		X		X	X			X	X	X	X	X
Direct Coombs test	X	X						X						X		X	X	X
Additional PD sample collection ⁿ		X						X						X		X	X	X
FCGR2A by buccal swab ^o		X																
RNA sequencing		X						X						X		X	X	X
Urine IgG		X						X						X		X	X	X

Immunophenotyping ^P		X								X					X		
Quantitative Coombs assay		X					X						X		X		
Adverse events	To be collected from the date that the ICF is signed through the last study visit																
Concomitant medications	To be collected from within at least 3 months prior to screening through the last study visit																

CIC = circulating immune complexes; d = day(s); ECG = electrocardiogram; ET = early termination; h = hour(s); *FCGR2A* = Fc gamma R2a receptor; HIV = human immunodeficiency virus; ICF = informed consent form; Ig = immunoglobulin; PD = pharmacodynamic; PK = pharmacokinetic; VZV = varicella-zoster virus.

- a. Visit Days 5, 12, and 19 may be conducted via at-home nurse in lieu of a subject visit to the study site.
- b. Complete physical examination, including weight, to be performed. Height and body mass index will be additional assessments conducted at screening.
- c. Vital sign measurements (sitting blood pressure, heart rate, respiratory rate, and oral temperature) to be obtained after 5 minutes of seated rest. Any abnormal measurements are to be repeated after 5 minutes of rest. On Days 0, 7, 14, 21, and 28, vital sign measurements will be collected immediately prior to the infusion; 15, 30, and 45 minutes after the start of the infusion; at completion of the infusion; and 30 minutes, 1 hour, and 2 hours following completion of the infusion.
- d. Pulse oximetry: On Days 0, 7, 14, 21, and 28, pulse oximetry to be measured immediately prior to the infusion; 15, 30, and 45 minutes after the start of the infusion; at completion of the infusion; and 30 minutes, 1 hour and 2 hours following completion of the infusion.
- e. Clinical safety labs: hematology, clinical chemistry, and urinalysis. See Protocol Section 6.7 for a complete list. Full clinical safety laboratory draws will be collected at screening and on Days 0, 7, 14, 21, 28, 33, 42, 56, 84, and 112. PD markers (albumin levels, hematocrit, hemoglobin, platelet count, reticulocyte count, lactate dehydrogenase, and total and indirect bilirubin) will be derived from the clinical safety laboratory results.
- f. Pregnancy test (women of childbearing potential only): To be performed at time of screening, prior to first dose of SYNT001 on Day 0, and on Days 56 and 112. Urine or serum test is acceptable; however, positive urine tests must be confirmed with serum testing.
- g. Digital 12-lead ECG to be obtained in triplicate at least 1 to 2 minutes apart and after 5 minutes of rest in a supine position. See Protocol Section 6.6 for additional information. On Days 0 and 28 to be obtained 5 minutes after the completion of infusion. Day 12 ECG will be collected only if the visit is conducted at the study site.
- h. Serology: Testing at Day 56 will not be done for any subject whose baseline titer is below the level of detection. If the Day 56 results are greater than 30% below the baseline value, or if the subject falls below the level of detection, the subject will be re-tested at Day 84; if still below the baseline value (or level of detection), the subject will be re-tested at Day 112. Any subject whose baseline value for tetanus or VZV was above the detectable level at baseline and is not within 30% of the baseline value or is below the detectable level by Day 112, will be referred to their primary care physician for further management. See Protocol Section 6.7.3 for additional information.
- i. PK: Starting on Days 0 and 28, serum samples will be collected just prior to the start of study drug infusion (pre-dose), and at 5 minutes and 2, 4, 6, 24, and 48 hours after the end-of-study drug infusion. Additional samples will be collected on Days 5 and 33. See Protocol Section 6.7.4 for additional information.
- j. Immunogenicity: Blood samples will be collected pre-dose when collected on dosing days. Samples will be collected on Days 0, 14, 28, 56, 84 and 112. See Protocol Section 6.7.6 for additional information.
- k. Prior to study drug infusion, SYNT001 drug product is to be diluted in dextrose 5% in water to a total volume of 250 mL and administered intravenously over 1 hour ±15 minutes using a 0.2-micron, inline filter. See Protocol Section 9 for additional information.
- l. Immunoglobulins (IgG, IgA, IgM) and IgG subtypes (IgG1-4): Collected for measurements of IgG, IgG subtypes (IgG1-4), IgA, IgM at every visit. On Days 0, 7, 14, 21, and 28, samples are collected prior to infusion of study drug.
- m. Subjects will return to the clinic on Days 84 and 112 for follow-up visits. Subjects whose total IgG is not within 30% of their Day 0 baseline value and not above 500 mg/dL at the Day 112 visit will be referred for further management.
- n. Additional PD samples to be collected for measurements of biomarkers, including D-dimer; antiphospholipid antibodies (lupus anticoagulant, anti-cardiolipin, and anti-beta-2-GP1 antibodies); antinuclear antibody titer; anti-double-stranded DNA antibody titer; complement component 3. See Protocol Section 6.7.5 for complete information.
- o. Buccal samples to be collected and stored.
- p. Immunophenotyping by flow cytometry for measurement of CD3⁺CD4⁺ T, CD3⁺CD8⁺ T, monocytes, natural killer (NK) cells, and B cells.

Table 3. Study Assessment for Cohort 2

Visit Number	Screening	Loading			Maintenance					Follow-Up		
	1	2	3	4	5	6	7	8	9	10	11	12
Time Point (Study Day)	-28 to -1	0 Baseline	7 (±1 d)	14 (±1 d)	28 (±3 d)	42 (±3 d)	56 (±3 d)	70 (±3 d)	84 (±3 d)	91 (±5 d) or ET visit	112 (±5 d)	140 (±5 d) EOS
Informed consent	X											
Demographics/medical history	X											
Inclusion/exclusion	X											
Physical examination ^a	X	X	X	X	X	X	X	X	X	X		X
Vital signs ^b	X	X	X	X	X	X	X	X	X	X	X	X
Karnofsky Performance Scale	X											
Pulse oximetry ^c		X	X	X	X	X	X	X	X			
Clinical safety labs ^d	X	X	X	X	X	X	X	X	X	X		X
Pregnancy test ^e	X	X			X					X		X
Hepatitis and HIV antibody screen	X											
12-lead ECG ^f	X	X		X	X					X		X
Tetanus and VZV antibodies ^g		X			X					X		X
Cold agglutinins (titer and thermal amplitude)		X			X					X		X
PK sampling ^h		X	X	X	X				X			
Immunogenicity ⁱ	X	X	X	X	X	X	X	X	X	X	X	X
Study drug administration ^l		X	X	X	X	X	X	X	X			
Immunoglobulins ^k	X	X	X	X	X	X	X	X	X	X ^l	X ^l	X ^l
CIC		X	X	X	X	X	X	X	X	X	X	X
Haptoglobin	X	X	X	X	X	X	X	X	X	X	X	X
Direct Coombs test	X	X		X	X					X		X
Additional PD sample collection ^m		X			X					X		
FCGR2A by buccal swab ⁿ		X										
RNA sequencing		X			X					X		

Immunophenotyping ^o		X			X					X		
Quantitative Coombs assay		X		X	X					X		
Adverse events	To be collected from the date that the ICF is signed through the last study visit											
Concomitant medications	To be collected from within at least 3 months prior to screening through the last study visit											

CIC = circulating immune complexes; d = day(s); ECG = electrocardiogram; EOS = end of study; ET= early termination; FCGR2A = Fc gamma R2a receptor; HIV = human immunodeficiency virus; ICF = informed consent form; Ig = immunoglobulin; PD = pharmacodynamic; PK = pharmacokinetic; VZV = varicella-zoster virus

- a. Complete physical examination, including weight, to be performed. Height and body mass index will be additional assessments conducted at screening only.
- b. Vital sign measurements (sitting blood pressure, heart rate, respiratory rate, and oral temperature) to be obtained after 5 minutes of seated rest. Any abnormal measurements are to be repeated after 5 minutes of rest. Vital sign measurements will be taken on all study visits. On dosing days, vital sign measurements will be collected immediately prior to the infusion; 15, 30, and 45 minutes after the start of the infusion; at completion of the infusion; and 30 minutes, 1 hour and 2 hours following completion of the infusion.
- c. Pulse oximetry: On dosing day, pulse oximetry to be measured immediately prior to the infusion; 15, 30, and 45 minutes after the start of the infusion; at completion of the infusion; and 30 minutes, 1 hour, and 2 hours following completion of the infusion.
- d. Clinical safety labs: hematology, clinical chemistry, and urinalysis. See Protocol Section 6.7 for a complete list. Full clinical safety lab draws will be collected at screening and at all study visits prior to infusion if applicable. PD markers (albumin levels, hematocrit, hemoglobin, platelet count, reticulocyte count, lactate dehydrogenase, and total and indirect bilirubin) will be derived from the clinical safety laboratory results.
- e. Pregnancy test (women of childbearing potential only): To be performed at time of screening and prior to dose on dosing days if applicable. Urine or serum test is acceptable; however, positive urine tests must be confirmed with serum testing.
- f. Digital 12-lead ECG to be obtained after 5 minutes of rest in the supine position and in triplicate approximately 1 minute apart. See Protocol Section 6.6 for additional information. On days of treatment, to be obtained 5 minutes after the completion of infusion.
- g. Serology: Any subject whose baseline value for tetanus or VZV was above the protective level at baseline and is not within 30% of the baseline value or is below the protective level by End of Follow-up, will be referred to their primary care physician for further management. See Protocol Section 6.7.3 for additional information.
- h. PK: Starting on dosing days, serum samples will be collected just prior to the start of study drug infusion (pre-dose) and at 5 minutes, 1 and 2 hours after the end of study drug infusion. See Protocol Section 6.7.4 for additional information.
- i. Immunogenicity: Samples will be collected pre-dose when collected on dosing days. See Protocol Section 6.7.6 for additional information.
- j. Prior to study drug infusion, SYNT001 drug product is to be diluted in dextrose 5% in water to a total volume of 250 mL and administered intravenously over 1 hour ±15 minutes using a 0.2-micron, inline filter. See Protocol Section 9 for additional information.
- k. Immunoglobulins (IgG, IgA, IgM) and IgG subtypes (IgG 1-4): Collected for measurements of IgG, IgG subtypes (IgG1-4), IgA, and IgM at every visit. On dosing days, samples are collected prior to infusion of study drug. See Protocol Section 6.7.5 for additional information.
- l. Subjects will return to the clinic on Days 91, 112, and 140 for follow-up visits. Subjects whose total IgG is not within 30% of their Day 0 baseline value and not above 500 mg/dL at Day 140 will be referred for further management.
- m. Additional PD samples to be collected for measurements of biomarkers, including D-dimer; antiphospholipid antibodies (lupus anticoagulant, anti-cardiolipin, and anti-beta- 2-GP1 antibodies); antinuclear antibody titer; anti-double-stranded DNA antibody titer; complement component 3. Collect samples pre-dose on dosing days. See Protocol Section 6.7.5 for additional information.
- n. Buccal samples to be collected and stored.
- o. Immunophenotyping by flow cytometry for measurement of CD3⁺CD4⁺ T, CD3⁺CD8⁺ T, monocytes, natural killer (NK) cells, and B cells. Collect samples pre-dose on dosing days.

Table 4. Study Assessments for Cohort 2; Alternative Weekly Maintenance Schedule

Visit Number	Screening	Loading			Maintenance										Follow-Up		
	1	2	3	4	5	6	7	8	9	10	11	12	13	14	15	16	17
Time Point (Study Day)	-28 to -1	0 Baseline	7 (±1 d)	14 (±1 d)	21 (±3 d)	28 (±3 d)	35 (±3 d)	42 (±3 d)	49 (±3 d)	56 (±3 d)	63 (±3 d)	70 (±3 d)	77 (±3 d)	84 (±3 d)	91 (±5 d) or ET Visit	112 (±5 d)	140 (±5 d) EOS Visit^q
Informed consent	X																
Demographics/medical history	X																
Inclusion/exclusion	X																
Physical examination ^a	X	X	X	X	X	X	X	X	X	X	X	X	X	X	X		X
Vital signs ^b	X	X	X	X	X	X	X	X	X	X	X	X	X	X	X	X	X
Karnofsky Performance Scale	X																
Pulse oximetry ^c		X	X	X	X	X	X	X	X	X	X	X	X	X			
Clinical safety labs ^d	X	X	X	X	X	X	X	X	X	X	X	X	X	X	X		X
Pregnancy test ^e	X	X			X										X		X
Hepatitis and HIV antibody screen	X																
12-lead ECG ^f	X	X		X	X										X		X
Tetanus and VZV antibodies ^g		X			X										X		X
Cold agglutinins (titer and thermal amplitude)		X			X										X		X
PK sampling ^h		X	X	X	X									X			
Immunogenicity ⁱ	X	X	X	X	X	X	X	X	X	X	X	X	X	X	X	X	X
Study drug administration ^j		X	X	X	X	X	X	X	X	X	X	X	X	X			
Immunoglobulins ^k	X	X	X	X	X	X	X	X	X	X	X	X	X	X	X ^l	X ^l	X ^l
CIC		X	X	X	X	X	X	X	X	X	X	X	X	X	X	X	X
Haptoglobin	X	X	X	X	X	X	X	X	X	X	X	X	X	X	X	X	X
Direct Coombs test	X	X		X	X										X		X
Additional PD sample collections ^m		X			X										X		

FCGR2A by buccal swab ⁿ		X															
RNA sequencing		X			X										X		
Immunophenotyping ^o		X			X										X		
Quantitative Coombs assay		X		X	X				X						X		
Adverse events	To be collected from the date that the ICF is signed through the last study visit																
Concomitant medications	To be collected from within at least 3 months prior to screening through the last study visit																

CIC = circulating immune complexes; d = day(s); ECG = electrocardiogram; EOS = end of study; ET= early termination; FCGR2A = Fc gamma R2a receptor; HIV = human immunodeficiency virus; ICF = informed consent form; Ig = immunoglobulin; PD = pharmacodynamic; PK = pharmacokinetic; VZV = varicella-zoster virus

- a. Complete physical examination, including weight, to be performed. Height and body mass index will be additional assessments conducted at screening only.
- b. Vital sign measurements (sitting blood pressure, heart rate, respiratory rate, and oral temperature) to be obtained after 5 minutes of seated rest. Any abnormal measurements are to be repeated after 5 minutes of rest. Vital sign measurements will be taken on all study visits. On dosing days, vital sign measurements will be collected immediately prior to the infusion; 15, 30, and 45 minutes after the start of the infusion; at completion of the infusion; and 30 minutes, 1 hour and 2 hours following completion of the infusion.
- c. Pulse oximetry: On dosing days, pulse oximetry to be measured immediately prior to the infusion; 15, 30, and 45 minutes after the start of the infusion; at completion of the infusion; and 30 minutes, 1 hour, and 2 hours following completion of the infusion.
- d. Clinical safety labs: hematology, clinical chemistry, and urinalysis. See Protocol Section 6.7 for a complete list. Full clinical safety lab draws will be collected at screening and at all study visits prior to infusion. PD markers (albumin levels, hematocrit, hemoglobin, platelet count, reticulocyte count, lactate dehydrogenase, and total and indirect bilirubin) will be derived from the clinical safety laboratory results.
- e. Pregnancy test (women of childbearing potential only): To be performed at time of screening and prior to dose on dosing days if applicable. Urine or serum test is acceptable; however, positive urine tests must be confirmed with serum testing.
- f. Digital 12-lead ECG to be obtained after 5 minutes of rest in the supine position and in triplicate approximately 1 minute apart. See Protocol Section 6.6 for additional information. On dosing days, to be obtained 5 minutes after the completion of infusion.
- g. Serology: Any subject whose baseline value for tetanus or VZV was above the protective level at baseline and is not within 30% of the baseline value or is below the protective level by End of Follow-up, will be referred to their primary care physician for further management. See Protocol Section 6.7.3 for additional information.
- h. PK: On dosing days if applicable, serum samples will be collected just prior to the start of study drug infusion (pre-dose) and at 5 minutes, 1 and 2 hours after the end of study drug infusion. See Protocol Section 6.7.4 for additional information.
- i. Immunogenicity: Samples will be collected pre-dose when collected on dosing days. See Protocol Section 6.7.6 for additional information.
- j. Prior to study drug infusion, SYNT001 drug product is to be diluted in dextrose 5% in water to a total volume of 250 mL and administered intravenously over 1 hour ±15 minutes using a 0.2-micron, inline filter. See Protocol Section 9 for additional information.
- k. Immunoglobulins (IgG, IgA, IgM) and IgG subtypes (IgG 1-4): Collected for measurements of IgG, IgG subtypes (IgG1-4), IgA, and IgM at every visit. On dosing days, samples are collected prior to infusion of study drug. See Protocol Section 6.7.5 for additional information.
- l. Subjects will return to the clinic on Days 91, 112, and 140 or ET for follow-up visits. Subjects whose total IgG is not within 30% of their Day 0 baseline value and not above 500 mg/dL at Day 140 will be referred for further management.
- m. Additional PD samples to be collected for measurements of biomarkers, including D-dimer; antiphospholipid antibodies (lupus anticoagulant, anti-cardiolipin, and anti-beta- 2-GP1 antibodies); antinuclear antibody titer; anti-double-stranded DNA antibody titer; complement component 3. Collect samples pre-dose on dosing days. See Protocol Section 6.7.5 for additional information.
- n. Buccal samples to be collected and stored.
- o. Immunophenotyping by flow cytometry for measurement of CD3⁺CD4⁺ T, CD3⁺CD8⁺ T, monocytes, natural killer (NK) cells, and B cells. Collect samples pre-dose on dosing days

Table 5. Timing window allowances for PK/PD sampling, ECG, and vital sign measurements at dosing visits

Time Point	Tolerance Window	
	Cohort 1	Cohort 2
Pharmacokinetic Sampling		
0 hour	-240 minutes to 0 hour	-240 minutes to 0 hour
5 minutes post end-of-infusion	±5 minutes	±5 minutes
1 hour post end-of-infusion	N/A	±15 minutes
2 hours post end-of-infusion	±15 minutes	±15 minutes
4 and 6 hours post end-of-infusion	±15 minutes	N/A
24 hours post end-of-infusion	±60 minutes	N/A
48 hours post end-of-infusion	±120 minutes	N/A
Pharmacodynamic (Immunoglobulins) Sampling		
0 hour	-240 minutes to 0 hour	-240 minutes to 0 hour
24 hours post end-of-infusion	±60 minutes	N/A
48 hours post end-of-infusion	±120 minutes	N/A
ECG		
5 minutes post end-of-infusion	±10 minutes	±10 minutes
Vital Signs^a		
0 hour	-240 minutes to 0 hour	-240 minutes to 0 hour
15, 30, and 45 minutes after start of infusion	±5 minutes	±5 minutes
At completion of the infusion	±10 minutes	±10 minutes
30, 60, and 120 minutes post end-of-infusion	±10 minutes	±10 minutes

Abbreviations: ECG = electrocardiogram; PD = pharmacodynamic; PK = pharmacokinetic.

^aVital signs to include blood pressure, pulse rate, respiratory rate, oral temperature, and pulse oximetry (Cohort 1 only).

Table 6. Pharmacodynamic Assessments

Parameter	Collection Time Points	
	Cohort 1	Cohort 2 ^a
Immunoglobulins: IgG IgG subtypes (IgG1-4) IgA IgM	Screening and Days 0, 1, 2, 5, 7, 12, 14, 19, 21, 28, 29, 30, 33, 42, 56, 84, and 112	Screening and Days 0, 7, 14, 28, 42, 56, 70, 84, 91, 112, 140
Circulating immune complexes (CIC)	Days 0, 5, 7, 12, 14, 19, 21, 28, 33, 42, 56, 84, and 112	Days 0, 7, 14, 28, 42, 56, 70, 84, 91, 112, 140
Albumin Hematocrit Hemoglobin Haptoglobin Platelet count Reticulocyte count Lactate dehydrogenase (LDH) Total and indirect bilirubin	Screening and Days 0, 7, 14, 21, 28, 33, 42, 56, 84, and 112	Screening and Days 0, 7, 14, 28, 42, 56, 70, 84, 91, 140
Direct Coombs test (also known as direct antiglobulin test [DAT])	Screening and Days 0, 14, 33, 56, 84, and 112	Screening and Days 0, 14, 28, 91, 140
D-dimer Antiphospholipid antibodies Lupus anticoagulant Anti-cardiolipin antibody Anti-beta-2-GP1 antibody Antinuclear antibody (ANA) titer Anti-dsDNA antibody titer Complement component 3 (C3)	Days 0, 14, 33, 56, 84, and 112	Days 0, 28, 91
RNA sequencing	Days 0, 14, 33, 56, 84, and 112	Days 0, 28, 91
Urine IgG	Days 0, 14, 33, 56, 84, and 112	NA
Quantitative Coombs assay	Days 0, 14, 33, and 56	Days 0, 14, 28, 91
Immunophenotyping by flow cytometry for measurement of; 
 • CD3⁺CD4⁺ T • CD3⁺CD8⁺ T • monocytes • NK cells • B cells 	Days 0, 28, and 56	Days 0, 28, 91
Cold agglutinins (titer and thermal amplitude)	Days 0, 33, 56, 84, and 112	Days 0, 28, 91, 140
FCGR2A SNP by buccal swab	Day 0	Day 0

^a Ongoing safety and PD evaluations may result in modification of the dosing regimen from every other week to weekly.

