## 6.5 Vital Sign Measurements

Vital sign assessments will include measurements of sitting blood pressure (mm Hg), heart rate (beats per minute), respiration rate (breaths per minute), pulse oximetry, and oral temperature (Celsius). Abnormal results are to be repeated after 5 minutes of rest. See [Table 5](#) for timing window allowances with respect to measurement collection.

When vital signs are to be collected at the same time point as a blood collection, vital signs should be collected first. Vital sign measurements will be collected after the subject has been sitting for 5 minutes. Subjects should be seated quietly for at least 5 minutes in a chair with their backs supported, their feet flat on the floor (legs uncrossed), and their arms bared on a hard surface, with the arm slightly abducted and bent, with palm up and the midpoint of upper arm at heart level. Correct cuff and bladder size should be utilized and the same cuff and arm should be used per subject throughout study.

Vital sign measurements are to be obtained immediately prior to the infusion; 15, 30, and 45 minutes after the start of the infusion; at completion of the infusion; and 30 minutes, 1 hour and 2 hours following completion of the infusion. Abnormalities in vital sign measurements will be graded in severity per the National Cancer Institute Common Terminology Criteria for Adverse Events (NCI CTCAE) scale Version 4.03.

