## 6.6 12-Lead Electrocardiogram (ECG)

On dose administration days, digital 12-lead ECG measurements will be obtained at 5 minutes after the completion of the infusion. When ECGs are to be collected at the same time point as a blood collection, ECGs should be collected first. ECGs are to be performed with the subject in a supine position having rested in this position for at least 5 minutes before each reading. ECGs are to be performed in triplicate at least 1 to 2 minutes apart (Cohort 1) or approximately 1 minute apart (Cohort 2). See [Table 5](#) for timing window allowances with respect to performing ECG.

The following ECG parameters will be collected: PR interval, RR interval, QRS interval, and QT interval. The ECG findings will be evaluated by a qualified physician for the presence of abnormalities (qualitative assessment). The physician will assess each ECG as normal, abnormal/not clinically significant, or abnormal/clinically significant.

Normal corrected QT interval using Fridericia’s formula QTcF is  $\leq 450$  msec.

Abnormalities in the ECG that appear following therapy or that result in clinical signs and symptoms are considered clinically significant for the purposes of this study and will be recorded on the AE eCRF.

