3.2.5 Vital Sign Measurements

Vital sign assessments will include measurements of sitting blood pressure (mm Hg), heart rate (beats per minute), respiration rate (breaths per minute), pulse oximetry, and oral

temperature (Celsius). Abnormal results are to be repeated after 5 minutes of rest. See [Table 5](#) for timing window allowances with respect to measurement collection.

Abnormalities in vital sign measurements will be graded in severity per the National Cancer Institute Common Terminology Criteria for Adverse Events (NCI CTCAE) scale Version 4.03.

3.2.6 12-Lead Electrocardiogram (ECG)

On dose administration days, digital 12-lead ECG measurements will be obtained at 5 minutes after the completion of the infusion. When ECGs are to be collected at the same time point as a blood collection, ECGs should be collected first. ECGs are to be performed in triplicate at least 1 to 2 minutes apart (Cohort 1) or approximately 1 minute apart (Cohort 2). See [Table 5](#) for timing window allowances with respect to performing ECG.

The following ECG parameters will be collected: PR interval, RR interval, QRS interval, and QT interval. The ECG findings will be evaluated by a qualified physician for the presence of abnormalities (qualitative assessment). The physician will assess each ECG as normal, abnormal/not clinically significant, or abnormal/clinically significant.

Normal corrected QT interval using Fridericia's formula QTcF is ≤ 450 msec.

Abnormalities in the ECG that appear following therapy or that result in clinical signs and symptoms are considered clinically significant for the purposes of this study and will be recorded on the AE eCRF.

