4.8 Analysis of Secondary Endpoints

4.8.1 Pharmacokinetic Analysis

PK results for SYNT001 will be summarized by cohort, visit and time point.

Descriptive statistics will be provided for the PK parameters including mean, SD, CV, median, minimum, and maximum.

For calculation of mean concentrations and generation of mean concentration-time profiles, all below the limit of quantification (BLQ) values will be set to zero except when an individual BLQ falls between 2 quantifiable values, in which case it will be omitted.

If there are values above the BLQ, but too sparse to allow full analysis, descriptive statistics will be performed on available values.

PK concentrations will be summarized descriptively at each nominal time point by cohort using n, mean, SD, percent coefficient of variation (CV%), standard error, median, minimum, maximum, geometric mean, geometric CV%.

Mean concentrations (\pm SD) of SYNT001 will be plotted on a linear and semi-logarithmic scale against nominal time points, by cohort. Individual concentration for each subject will be plotted using original scale and semi-log scale.

Study drug serum concentration data will be used to calculate the following PK parameters, if feasible:

Parameters	Description
C_{\max}	Maximum observed plasma concentration observed directly from data at Day 0 and Day 28
T_{\max}	Time to reach maximum observed concentration directly from data at Day 0 and Day 28
λ_z	Apparent first-order terminal elimination rate constant calculated by linear regression of the terminal linear portion of the log concentration vs. time curve at Day 0 and Day 28
$t_{1/2}$	Terminal elimination half-life, calculated as $\ln(2)/\lambda_z$ at Day 0 and Day 28
AUC_{0-24}	AUC from time zero to 24 hours post-dose administration at Day 0 and Day 28
AUC_{∞}	AUC from time zero to infinity time (as $AUC_{0-t} + C_{\text{last}}/\lambda_z$, where C_{last} is the last quantifiable concentration) at Day 0 and Day 28

Actual sampling time will be used for PK calculations. Actual sampling times that are outside the scheduled sampling times window described in [Table 5](#) will be excluded from summary statistics of average PK SYNT001 serum concentrations but will still be used in the calculation of PK parameters.

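### Table 5 closes the 5-minute PK window at +10 minutes but lets the ECG that should precede it run to +15, so compliant conduct can push the first post-infusion sample out of the concentration summary

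*SAP*

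**What the plan says.** Protocol Table 5 and SAP Table 5 (Appendix A) carry the same tolerances. Both list the PK sample and the ECG at "5 minutes post end-of-infusion". The PK row reads "5 minutes post end-of-infusion ±5 minutes ±5 minutes" and the ECG row "5 minutes post end-of-infusion ±10 minutes ±10 minutes", with Cohort 1 first and Cohort 2 second.

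On order, SAP 3.2.6, like Protocol 6.6, states: "When ECGs are to be collected at the same time point as a blood collection, ECGs should be collected first". The ECG is a triplicate. Successive tracings are at least 1 to 2 minutes apart in Cohort 1 and about 1 minute apart in Cohort 2. Protocol 6.6 also requires the subject to be supine, "having rested in this position for at least 5 minutes before each reading".

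On analysis, SAP 4.8.1 says that PK samples taken outside the Table 5 windows "will be excluded from summary statistics of average PK SYNT001 serum concentrations". The same sentence keeps them for the calculation of PK parameters, for which actual times are used.

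**The concern.** Two procedures share one nominal time. The one that should go first has the later closing time, and the one that should go second is the one whose value is removed when it is late. A site can respect the order rule and the ECG window and still produce a PK sample that the SAP excludes.

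At stake is the 5-minute row of the concentration table and the matching point on the mean profile. This is the first draw after the infusion, in cohorts of at most 8 and 12 subjects. A value excluded there still feeds Cmax and Tmax, so the mean 5-minute concentration and the mean Cmax of one cohort could rest on different sets of subjects without any error by the site.

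**Working it through.** **Windows, in minutes after the end of infusion (Table 5)**

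- PK: 5 ± 5, so 0 to +10.
- ECG: 5 ± 10, so −5 to +15.
- Stretch in which an ECG is in window but a PK draw after it is not: 15 − 10 = 5 minutes.

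**Length of the triplicate.** Three tracings have two gaps between them, so the span is 2 × spacing + 3 × recording time. The spacing comes from Protocol 6.6 and SAP 3.2.6. The documents give no recording time, so 0 to 1 minute per tracing is assumed, with the gap counted from the end of one tracing to the start of the next.

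| Spacing | Recording time per tracing | Span | End if started at +5 | Latest start that ends by +10 |
|---|---|---|---|---|
| 1 min | 0 | 2 | +7 | +8 |
| 1 min | 0.5 | 3.5 | +8.5 | +6.5 |
| 1 min | 1 | 5 | +10 | +5 |
| 2 min | 0 | 4 | +9 | +6 |
| 2 min | 0.5 | 5.5 | +10.5 | +4.5 |
| 2 min | 1 | 7 | +12 | +3 |

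On the documents' own figures (recording time 0), an ECG started on time leaves 10 − 9 = 1 to 10 − 7 = 3 minutes for the draw. With 0.5 to 1 minute per tracing, Cohort 1 at 2-minute spacing misses the PK window even when the ECG starts at its nominal time.

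**Visits affected.** The conflict needs a post-infusion ECG and a PK draw on the same day. From the schedules of assessments these are Cohort 1 Days 0 and 28 and Cohort 2 Days 0, 14 and 28 (Days 0, 14 and 21 on the weekly alternative). Cohort 2 Days 7 and 84 have PK but no ECG and are not affected.

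**What the exclusion costs.** With 8 subjects in Cohort 1 and an unchanged SD, losing one value multiplies the standard error by √(8/7) = 1.07, and losing two by √(8/6) = 1.15.

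**What the exclusion gains.** The relative change in concentration over a delay d is 1 − 2^(−d/half-life). The documents give no half-life, so a single-exponential decline over a range of half-lives is assumed.

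- d = 5 min, 100 h: 0.06%.
- d = 15 min, 24 h: 0.7%.
- d = 15 min, 12 h: 1.4%.

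If these assumptions hold, a draw 5 to 15 minutes late carries almost the same concentration as one on time.

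**The case against.** The strongest reply is that nothing forces the conflict. The ECG window opens before the infusion ends, and so does the ±10-minute window for the completion vital signs. A site could take seated vital signs at −5, rest the subject supine from −5 to 0, record the triplicate from 0 to +4 and draw PK at +5. Every tolerance is then met. The order rule also says should rather than must, and the collection details sit in a laboratory manual (Protocol 6.7.4) that may settle the order. All of this stands. A reader who infers that the PK window always closes before the ECG can be finished goes further than Table 5 allows.

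Two other stronger readings are also unsupported.

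- *Selective loss of subjects with abnormal vital signs.* Protocol 6.5 says "Abnormal results are to be repeated after 5 minutes of rest". If the completion reading were repeated and the ECG held until afterwards, the ECG would start at about +10 and PK would be late. But no section places the completion vital signs, or their repeat, before the ECG. Completion and 5 minutes post-infusion are separate rows in Table 5, so the selection argument depends on an order that the documents do not state.
- *A loss rate read off the window widths.* A triplicate that must finish by +15 can start from −5 to +13 (18 minutes) or to +11 (16 minutes). The last 5 of these minutes make PK late: 5/18 = 28% or 5/16 = 31%. This is a share of permitted start times, not a probability, because sites aim for +5.

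It is also fair to say that the PK endpoints named in SAP 2.1.2 are parameters, and those keep the late sample.

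**Conclusion.** The point holds as a low-severity inconsistency. A triplicate finishing between +10 and +15 obeys its own window and the order rule, and the PK draw that follows is always out of window and excluded under SAP 4.8.1. On the stated spacings the slack after an on-time ECG is 1 to 3 minutes, and it shrinks or disappears once recording time is allowed for.

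The damage is confined to the 5-minute concentration summary and the mean profile at the visits listed. Cmax, Tmax and, in Cohort 1, AUC are unaffected by the exclusion. How often it would happen cannot be derived from the documents. It is tempting to call the lost value the peak, but no section labels it so; it is the first post-infusion draw. That the exclusion gains little accuracy rests on the assumed single-exponential half-life of 12 h or longer.

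**What to change.** Reconcile the order rule with the tolerances in one of three ways.

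1. Extend the 5-minute PK window in both copies of Table 5, for example to 0 to +20 minutes with the actual time recorded. This leaves 5 minutes after an ECG that finishes at +15. It stays clear of the next PK windows, which open at 60 − 15 = 45 minutes in Cohort 2 and 120 − 15 = 105 minutes in Cohort 1.
2. State that at this one time point the PK draw precedes the ECG.
3. If the protocol is not amended, add a sentence to SAP 4.8.1 that a first post-infusion sample taken up to +20 minutes stays in the 5-minute concentration summary.

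It would also help to say whether the ECG window applies to the first tracing or to the whole triplicate. A first tracing at +15 would end at +17 to +19 before recording time.

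No new samples are needed. The price is a slightly wider spread of actual times at this point: under about 1.5% in concentration for delays of up to 15 minutes, on the half-life assumption above. Options 1 and 2 change protocol text and so need a minor modification under Protocol Section 14, which provides for IRB review with an exception for purely logistical or administrative changes. Option 3 needs only the SAP.
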